care, we will complete serial blood pressures in order to finalize eligibility for the study. These serial blood pressures will be used as the baseline measurements for the study if the average systolic blood pressure is 130 or greater. If the patient has eligible blood pressures, randomization to a study arm will then take place. Randomization lists for each site stratified by race (Black and White) will be prepared by the statistician and randomization will be performed as soon as eligibility and consent is confirmed. See Figure 4 for PACESETTER flow chart. Height weight and mid-arm circumference measured. A set of questionnaires will be administered (see Table 3). If the patient is consented and is unable to be seen in person, the SBP will be confirmed either verbally over the telephone while the patient performs the BP protocol, visually via televisit, or visually with a text message sent to study staff from patient. If the patient does not have a cuff at home, study staff will: 1) coordinate with home health to have blood pressures taken, 2) use bp measurements from the most recent clinic in person appointment, or 3) direct the patient to the closest pharmacy with a bp cuff that they can use to take a bp with study staff on the phone. If bp is not able to be obtained, the patient will not be eligible for this study. Wrist cuffs are acceptable for enrollment BP measurements. Height, weight and mid-arm circumference will be confirmed verbally from patient (if possible) or the most recent medical record data will be used. Patients will complete various forms showing that they can use the med device, BP monitor, phone and app properly. If the patient cannot sign his or her own name, the patient will make a mark as part of the consent process and a witness will sign the consent document as well.

Figure 4. PACESETTER Intervention Group Flow

E.5.3. Intervention Group

The proposed PACESETTER intervention (see Figure 4) was developed based on preliminary data, practical experience and a comprehensive literature review including the published experiences of the PACESETTER investigative team.

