ii. Body Mass Index (BMI): BMI will serve as a measure of weight loss. Height and weight will be measured without shoes using a tape rule and a validated digital scale respectively. All measurements will be recorded to the nearest 0.1 inch and 0.1 lbs (If patient is unable to be seen in person, study staff will confirm height and weight with patient if possible or use most recent data from medical records).

E.5.5.2. Self-report Measures and Other Information

i. Patient demographics: Socio-demographic data will be used to describe the cohort & examine effects of these factors on outcomes.

ii. Cardiovascular (CVD) Emergency department encounters and re-hospitalizations: will be used to compare health system utilization rates during study. CVD encounters will be based on International Classification of Disease, 9th Revision (ICD-9) codes for the primary discharge diagnosis, categorized as either heart disease or cerebrovascular disease hospitalizations. Heart disease hospitalizations will include those for hypertension (ICD codes 401 to 405), acute coronary artery disease (410, 411), chronic coronary artery disease (412 to 414), dysrhythmia (427), and congestive heart failure (428). Cerebrovascular disease (ICD codes 430 to 438). A statistician blinded to study group assignment will assess the occurrence of these encounters in the SC Inpatient Hospital Discharge Database. All hospitals in SC, with the exception of military & federal institutions, are mandated to provide data on every hospitalization, including demographic information, dates & type of hospitalization, & discharge disposition. SC's Office of Research & Statistics collects these data & freely provides investigators with a patient-based hospitalization database. We have experience using this database.⁵⁸

iii. Medication adherence: Adherence to prescribed antihypertensive drugs will be assessed using the Modified Adherence to Refills and Medications Scale. Medication adherence will also be calculated for all subjects using med possession ratios (MPRs),¹²³ on all HTN meds at each evaluation and an overall MPR score will be calculated. PACESETTER subjects will have their Viaca based monthly medication adherence scores as their primary measure of medication adherence. All participants in the study will also be contacted by the research staff via phone call at months 2, 6, and 10 to ask you to complete a medication count.

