iv. Chart extraction: Information extracted from the medical records will include medications and their dosages, biomarker measurements from clinic visits, and medical comorbidities.

E.5.5.3. Vascular Events (Specific Aim 3)

PACESETTER aims to collect any vascular events that take place while a patient is in the trial. This is being done to ensure that all events are captured in a timely fashion without any recollection biases. In order to do this, all participants & families will be urged to contact the RC as soon as any event that might be a CVD event

Program to Avoid Cerebrovascular Events through Systematic Electronic Tracking and Tailoring of an Eminent Risk-factor (PACESETTER)

has occurred. CVD events will include stroke, transient ischemic attack, or an acute coronary syndrome. Participants with potential CVD events will be evaluated by a study physician within 48 hours. If the history or the exam indicates that a stroke might have taken place, all clinical, laboratory & imaging data needed to confirm the event will be obtained by the RC & sent to a blinded physician adjudicator assigned to each site (see letters of support), for independent review. Final reports regarding the event will be sent to primary research site (MUSC) within 15 days. Participants with events will continue to be followed at scheduled intervals. These are study-specific steps the patient or caregiver will be asked to take once the CVD event has been addressed medically- ie, after the condition been treated and stabilized.

E.5.6. Statistical Considerations

E.5.6.1. Randomization

Once eligibility, consent & baseline data are confirmed, participants will be randomly assigned to PACESETTER intervention vs. usual care in a 1:1 allocation ratio, stratified by race (Black and White) & study site. An adaptive block randomization scheme will be developed & maintained by the lead study biostatistician. Once a patient is randomized he or she will be entered into the study and included in intent-to-treat analysis. The randomization assignment will be known to the project coordinator, and the statistician in charge of the randomization procedure, but not known to the research assistant who will be conducting participant follow-up assessments.

E.5.6.2. Power and Sample Justification

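### E.5.2 and E.5.6.1 set different triggers for randomisation; read literally, E.5.2 lets self-reported baselines be collected after allocation

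*Combined protocol and SAP*

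**What the plan says.** Section E.5.2 (Recruitment) states the trigger twice. After the serial blood pressures it says: "If the patient has eligible blood pressures, randomization to a study arm will then take place". The next sentence, on the randomisation lists, adds that "randomization will be performed as soon as eligibility and consent is confirmed". Neither statement makes completed baseline data a condition. The text then points to Figure 4 and continues with "Height weight and mid-arm circumference measured" and "A set of questionnaires will be administered (see Table 3".

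Section E.5.6.1 (Randomization) has a third condition: "Once eligibility, consent & baseline data are confirmed, participants will be randomly assigned to PACESETTER intervention vs. usual care in a 1:1 allocation ratio".

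For blood pressure the two sections agree. E.5.2 says of the eligibility readings: "These serial blood pressures will be used as the baseline measurements for the study if the average systolic blood pressure is 130 or greater".

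Table 3 (E.5.5) has a baseline column that covers more than blood pressure. It includes medication adherence, BMI and self-management as secondary outcomes, and depression, hypertension and stroke knowledge, health literacy and disability among the mediators. E.5.5.2 describes the adherence instrument: "Adherence to prescribed antihypertensive drugs will be assessed using the Modified Adherence to Refills and Medications Scale".

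Section E.5.7.1 models all outcomes by regression adjusted for baseline factors found to be imbalanced after randomisation, and compares the result with an unadjusted analysis.

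**The concern.** A baseline is protected by randomisation only if it is fixed before the patient can know the arm. Patients cannot be blinded in this trial, and the content of the arms bears directly on what the questionnaires ask. Under E.5.3.1, intervention patients receive adherence criteria, device training and messages about hypertension and stroke. Under E.5.4, the control messages avoid those subjects. A patient who answers an adherence or self-management scale after learning the arm may answer it differently.

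Two kinds of result would be exposed. The first is the adjusted or change-over-time effect on a self-reported secondary outcome, which uses the affected value as its reference. The second is any model in which an affected variable becomes a covariate. The selection rule in E.5.7.1 makes the second route more likely, because arm-aware answering can itself produce the imbalance that triggers adjustment.

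**Working it through.** The point rests on comparing the text. The plan gives no figure to reproduce, and alpha, power and sample size do not depend on it.

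1. **Triggers side by side.** E.5.2: eligibility and consent, acted on at once. E.5.6.1: eligibility, consent and baseline data. A site that randomises at the moment E.5.2 names, with questionnaires outstanding, complies with E.5.2 and breaches E.5.6.1.

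2. **Could baseline data in E.5.6.1 mean blood pressure only?** The term is not defined, and this reading would reconcile the sections. But the baseline blood pressure is the same set of readings that completes eligibility in E.5.2, so the third condition would then add nothing to the first. Table 3 also lists many other baseline items. The wider reading is the more natural one.

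3. **Which baselines are exposed?**
   - SBP: taken before randomisation under both sections, so not exposed.
   - Height and weight: E.5.2 mentions them after randomisation, but E.5.1 excludes BMI above 40, so a measured or chart value should already exist. Weak exposure.
   - Modified Rankin score: a score of 3 or more is an exclusion in E.5.1, so it too should be known beforehand.
   - Adherence scale and self-management: secondary outcomes, and the main exposure.
   - Depression, knowledge and other self-reported mediators: exposed only if they enter a model as covariates. Depression is measured at baseline only.

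4. **How a shifted baseline would carry through.** Let d be the shift in the baseline mean of one arm caused by knowing the allocation, in SD units, and b the slope of follow-up on baseline. The bias in the baseline-adjusted effect has absolute size b × d. For an analysis of change from baseline it is d. The documents give neither b nor d.

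5. **Illustration only.** Assume d from 0 to 0.3 and b from 0.3 to 0.7.
   - d = 0: bias 0.
   - d = 0.1, b = 0.3: 0.3 × 0.1 = 0.03 SD.
   - d = 0.3, b = 0.7: 0.7 × 0.3 = 0.21 SD.
   - Change from baseline: 0 to 0.3 SD.

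   For scale, take the 80 per arm of E.5.6.2 and treat b as the correlation r. The standard error of the adjusted effect is √(2/80) × √(1 − r²). At r = 0.3 this is 0.158 × 0.954 = 0.151 SD, and at r = 0.7 it is 0.158 × 0.714 = 0.113 SD. The two non-zero cases are then 0.03/0.151 = 0.2 and 0.21/0.113 = 1.9 standard errors. The range begins at zero, because nothing in the documents shows that patients would learn their arm before answering.

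**The case against.** The strongest reply is that the order of sentences in E.5.2 is not a timeline. The same paragraph goes on to describe remote confirmation of blood pressure and how a patient unable to sign gives consent. Both must come before randomisation, yet both are printed after it. This stands: the position of the questionnaires proves nothing by itself. What remains is the wording of the trigger, which requires randomisation once eligibility and consent are in hand and does not wait for the questionnaires.

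Second, the section devoted to randomisation already has the sounder rule. That is true, and it is why the correction is small. It does not tell a site which of the two rules to follow.

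Third, E.5.5 has assessors blinded to arm perform all study measurements, and E.5.6.1 limits knowledge of the assignment to the project coordinator and the randomisation statistician. So a reader should not infer that staff collecting baselines would know the arm. Assessor blinding does not, however, protect answers given by a patient who knows it. The documents do not say when patients are told.

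Fourth, Figures 3 and 4 are not visible in the text reviewed, and E.10 plans a manual of operations. Either might settle the order. For the same reason, a reader might infer that sites work from E.5.2 rather than E.5.6.1, but the documents do not say so.

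Finally, adherence is also measured by possession ratios and medication counts (E.5.5.2), and adjusted results are to be set beside unadjusted ones. Both limit the consequences.

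**Conclusion.** The two sections conflict on when a patient may be randomised, and nothing in the available text reconciles them. Read literally, E.5.2 permits self-reported baselines to be collected after allocation. This is an internal inconsistency worth correcting, with limited reach: chiefly the adherence scale and self-management, plus self-reported mediators if they are chosen as covariates. An adjusted SBP model could be touched only through such a covariate.

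A reader might go further and conclude that E.5.2 requires questionnaires after allocation, or that the secondary effects will be biased by a known amount. The documents support neither. The sequence is permitted, not prescribed. The illustrative 0.03 to 0.21 SD rests wholly on assumed values, and zero is equally compatible with the text.

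The conclusion assumes that baseline data in E.5.6.1 means more than blood pressure, and that the unseen figures and planned manual do not already fix the order.

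**What to change.** In E.5.2, replace both statements of the trigger with the one in E.5.6.1, and define baseline data there as all items in the baseline column of Table 3. State that the assignment is released only when three things are complete in REDCap: eligibility (including BMI and modified Rankin score), consent, and all Table 3 baseline measures.

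State also that intervention-arm onboarding follows allocation. This covers the device and app demonstration and the beliefs, values and life-goals questionnaire of E.5.3.1, which serves message tailoring and belongs to that arm alone. Bring Figure 4 and the manual of operations into line if they show another order.

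The cost is a few reworded sentences and one completeness check in a data system the trial already uses (E.5.7.2). No procedure or visit is added and the sample size is unchanged.

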To control for attention exposure, the control group will get SMS messages dealing with healthy lifestyle behaviors (smoking, diet, physical activity) but not with med adherence, HTN or stroke related issues. Messages will be same frequency & size as PACESETTERS' motivational/ reinforcement messages for medication adherence. Every 3 days (comparable to PACESETTERS BP monitoring) they will receive an automated SMS directing them to a different 2-3 minute video/YouTube™ clips on healthy lifestyles. For those who prefer hard copy material, brochures (esp. novella format) will be mailed across the trial. SC and PACESETTER physicians will receive same expert consensus guideline charts. Patients in this arm of the study will receive usual care as determined by their providers. Usual care after stroke in the region typically involves at least one scheduled follow-up clinic visit after the initial diagnostic encounter with a neurologist, with subsequent care by a neurologist or primary care physician based on need. However, these patients will be encouraged to follow up with their primary care providers for the treatment of their stroke. SC subjects will also be contacted by phone monthly to confirm contact information and to inquire about hospitalizations. If the participant requests information, study staff will

Program to Avoid Cerebrovascular Events through Systematic Electronic Tracking and Tailoring of an Eminent Risk-factor (PACESETTER)

provide/send relevant materials and will be instructed to check with their primary care provider. Similar to the IG, the patient will have a total of 3 follow-up study visits (phone call visits/televisits will be available for patients unable to follow up in person) during which various study outcomes (see Figure 2) will be assessed.

E.5.5. Outcome and Mediator Measures

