Primary outcome is systolic BP at 12-months, which is the major modifiable step to stroke event rate reduction. A secondary analysis will examine whether PACESETTER improved systolic BP by a clinically significant amount. Also apart from the 12 month primary outcome, we will also conduct a longitudinal comparisons of systolic BP in IG vs. SC over the course of followup evaluations. Participants will be given an appointment encounter solely for collecting evaluation data at the times listed in Figure 2. Trained assessors blinded to the randomization arm (with no contact with PACESETTER clinical team and instructed not to infer and probe on the intervention) will perform all study measurements. Potential mediator/moderators of risk factor control will also be collected. If a patient endorses severe depressive symptoms, patient will be referred to the appropriate medical professional.

Table 3. PACESETTER Outcomes and Mediators

Outcome Type	Measurements	Assessment Duration	Target Goal	Baseline	4 months	8 months	12 months
Primary	Systolic blood pressure ^{173,174}	<15 mins	< 130 mmHg	X	X	X	X
Secondary	Cardiovascular ED encounters and re-hospitalizations	<10 mins	Group differences	X	X	X	X
	Medication adherence ¹²⁵	<10 mins	Group differences	X	X	X	X
	Body mass index ¹²⁶	<5 mins	Group differences	X	X	X	X
	Self-management ^{127,128}	<10 mins	Group differences	X	X	X	X
Tertiary	Stroke, Myocardial infarction, Death	<10 mins	Group differences	N/A	X	X	X
Mediators	Age, education, income, depression, ^{129,130}	<5 mins	Group differences	X	N/A	N/A	N/A
	HTN/stroke Knowledge, ^{131,132} Health literacy, ^{133,134} disability, ^{135,136} and study site	<10 mins	Group differences	X	X	X	X
	Side effects, Adverse events (as reported)	<10 mins	Group differences	X	X	X	X

E.5.5.1. Physiological/Laboratory Measures

i. BP measurements: Three readings will be taken by trained assessors (if patient is unable to be seen in person, trained assessor will confirm the readings are taken correctly by patient either by verbal confirmation of procedures or visually watching the patient complete the BP measurements) using an automated BP monitor with the patient seated comfortably for 5 min prior to the measurements, following guidelines.^{137,138} Average of the last two BP readings will be used as the measure for each visit. Uncontrolled BP is defined as average clinic systolic BP ≥ 130 mm Hg or diastolic BP ≥ 90 mmHg per guidelines.¹³⁷

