Our sample size calculation and power analyses are based on a 12 month change in the primary outcome of SBP, the premier modifiable risk factor for stroke. Large meta-analyses of observational and RCTs have found clinical benefit for having a SBP as low as 115 mm Hg. In addition, a large RCT of SBP-lowering for secondary stroke prevention found similar health benefits for persons with baseline HTN and for persons with baseline normotension. Data from MUSC clinic registry showed that the mean SBP for persons with SBP>120mmHg was 154.5 +/-10.3 mmHg. Using a type I error of 0.05, a power of 92%, a robust correlation of 0.8 between baseline and 12-months outcomes, no change in mean SBP in the control arm from baseline to 12 months and a two-sided test, 80 subjects in each treatment arm (or 160 subjects in total) will enable detection of a net decrease of 0.5 standard deviation units (which correspond to a difference of 8.8 mm Hg in SBP). This difference of 8.8 mm Hg in SBP between the two treatments is smaller than the 10 mm Hg threshold cited in the guideline, and thus we have sufficient statistical power with the estimated sample size to detect clinical benefit. An alternative outcome measure to SBP is recurrent stroke, but our sample size is not large enough to detect differences in recurrent stroke over 12-months of follow-up. Although we will facilitate the retention of subjects in the RCT as much as possible, the retention rates in disadvantaged populations are likely lower than in other settings. Assuming 20% loss to follow up, the conservative target for enrollment is 200. Data from MUSC indicated that 85% of all the patients at 3 days post-stroke had a SBP > 120. Thus, we conservatively expect ~50% will not meet eligibility criteria or may decline to participate, so we can potentially recruit over 200 patients including half of whom will be African Americans from the 2 sites over 3 years.

E.5.7. Data Management and Analysis

E.5.7.1. Analysis

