Descriptive statistics will be computed for all study variables, including average follow-up time, retention rate, protocol deviations and violations, and will be compared by treatment group. We will use t-test for continuous variables and chi-square test for categorical variables to make comparisons between two groups and corresponding ANOVA for more than two groups. The primary analysis will be performed according to the principle of intention to treat. All outcomes will be modeled using regression analyses adjusted for baseline factors that show imbalance after randomization and compared to analysis that does not adjust for residual baseline differences.^{140,141} A nominal p value of 0.05 or less will be considered as statistically significant in the primary analysis. Analysis of covariance (ANCOVA) will be used to test the hypotheses in Aim 2 adjusting for baseline differences. Assessment of the fit of the models will be made using residual and diagnostic plots. We will employ longitudinal data methods (generalized linear mixed models [GLMM]),¹⁴² which account for correlation of outcomes due to repeated measurements and clustering by site and missing at random (MAR) data to study the change in outcomes over time between the two groups. In addition, to evaluate sensitivity of study conclusions to missing data, we will use multiple imputation methods to estimate single end-point outcome measures and carry out analyses on the complete data set using the MNAR statement in SAS 9.4. If we suspect violation of MAR then we will do additional sensitivity analysis.¹⁴³ Trajectory or change over time in BP and other related outcomes will be modeled via GLMM. Differences in time to recurrent events between the two groups will be compared using a log-rank test and a Cox proportional hazards (PH) model (we will test for the PH assumption) will be used to adjust for observed confounders. Since all participant data will be included in this analysis, participants missing outcome data will be censored at the last follow-up assessment time. Exploratory analyses will also be performed by sub-groups (e.g. age, gender, race) to determine if any differential efficacy exists. If statistically significant differences are found between IG and CG arms, we will conduct regression analyses further adjusted by variables selected based on a combination of clinical judgment and descriptive statistical findings comparing

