We have chosen a one year primary time point to balance maximizing study follow up with studying a clinically useful time period of adherence. Multiple tactics will be used to facilitate high IG patient retention including obtaining full contact information for patients, caregivers, and relatives at time of enrollment and updating every 3 months. Follow-up visits will be scheduled, whenever possible, on days subjects already have scheduled clinic visits or plan to visit the city. Research Nexus will be used as an additional location to complete study visits as needed. Phone call visits and televisits will be available if patients are unable to return to in-person visits. We will seek the guidance of PTF regarding all recruitment and retention strategies. Strategies will include regular telephone and mail contacts; in the CG these will not include material regarding stroke-related health care issues. Participants are receiving modest monies (\$50 per encounter, an additional \$50 for completing all study visits, and \$75 upon completion of KII interview) for being in the trial.

E.9.2. Individual Randomization

Program to Avoid Cerebrovascular Events through Systematic Electronic Tracking and Tailoring of an Eminent Risk-factor (PACESETTER)

We are randomizing patients instead of clusters, because it is the most statistically efficient method for showing efficacy and thus would require the smallest sample size.¹⁶⁵ Cluster randomization is appropriate when contamination threat is high,¹⁶⁶ but we believe the contamination threat is relatively small in this study.

E.9.3. Missing Data

Beyond attrition (wholly missing follow up assessments), we anticipate little missing data. Under the assumption of MAR, our analyses approach yields intent-to-treat parameter estimates that are consistent with what would be expected if there were no missing data. We will conduct secondary analyses of all hypotheses using only patients with complete data for comparison to the primary intent-to-treat analyses. The degree to which results differ (vs. not) between these two analyses will be reported. If the results differ, it will not be possible to determine which is “true.” Our position will be to emphasize the intent-to-treat results for both substantive and statistical (preservation of randomization) reasons.

E.9.4. Representativeness

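### A monthly hospitalization enquiry is stated for the standard-care arm only, so active prompting for Aim 3 events differs by arm; the likely effect is small and its net direction uncertain

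*Combined protocol and SAP*

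**What the plan says.** Section E.5.4, on the standard-care arm: "SC subjects will also be contacted by phone monthly to confirm contact information and to inquire about hospitalizations". The same section matches the visits across arms: "Similar to the IG, the patient will have a total of 3 follow-up study visits". Sections E.5.3.1 and E.5.3.2, on the intervention arm, describe messages, device uploads, weekly reports and a call when a blood pressure threshold is crossed. They state no periodic enquiry about hospitalizations.

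Aim 3 events are collected in two ways that are common to both arms. Table 3 lists "Stroke, Myocardial infarction, Death" at 4, 8 and 12 months. Section E.5.5.3 adds volunteered reporting: "all participants & families will be urged to contact the RC as soon as any event that might be a CVD event" has occurred. It gives the purpose as follows: "This is being done to ensure that all events are captured in a timely fashion without any recollection biases". Possible strokes then go to a blinded adjudicator.

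Two other contacts are mentioned. Section E.5.5.2 gives all participants calls at months 2, 6 and 10, for a medication count. Section E.9.1 says: "Strategies will include regular telephone and mail contacts; in the CG these will not include material regarding stroke-related health care issues". Neither is said to ask about events.

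Section E.5.7.1 plans a log-rank test and a Cox model for time to recurrent events, and says that "participants missing outcome data will be censored at the last follow-up assessment time".

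**The concern.** If one arm is asked every month whether it has been in hospital and the other is asked every four months, the chance that an event is recorded depends on the arm. Blinded assessors and a blinded adjudicator do not cure this, because they work only on events that have been reported.

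For a participant who completes follow-up the difference matters little, since the next visit can still find the event. It matters for dropouts. Take a participant admitted at month 5.5 and lost at month 7. In standard care, the month 6 call can reveal the admission. In the intervention arm, unless someone volunteers it, the participant is censored event-free at month 4.

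At stake is the exploratory Aim 3 comparison and the plan's own wish to avoid recall bias in it.

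**Working it through.** **Contacts stated to ask about admissions or events**

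| | Intervention | Standard care |
|---|---|---|
| Visits (Table 3) | months 4, 8, 12 | months 4, 8, 12 |
| Monthly hospitalization calls (E.5.4) | none stated | up to 12 |
| Longest gap between enquiries | 4 months | 1 month |

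**Inputs.** The loss rate is from section E.5.6.2: "Assuming 20% loss to follow up, the conservative target for enrollment is 200". That figure reproduces: 160 / (1 − 0.20) = 200, or 100 per arm at 1:1.

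**Assumptions not in the plan:**
- Losses are spread evenly over 12 months.
- Events are missed only between a dropout's last enquiry and the loss.
- Every vascular event leads to an admission that the standard-care call would find.
- There is no true treatment effect.

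**Follow-up per 100 patients at 20% loss:** 80 × 12 + 20 × 6 = 1,080 person-months.

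**Unqueried time** = number lost × half the gap between enquiries:
- Intervention: 20 × 4/2 = 40 person-months (40/1,080 = 3.7%)
- Standard care: 20 × 1/2 = 10 person-months (0.9%)

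Events can therefore be found over 1,080 − 40 = 1,040 person-months in the intervention arm and 1,080 − 10 = 1,070 in standard care.

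**Rate ratio, intervention to standard care.** Section E.5.7.1 does not say whether a monthly call counts as a follow-up assessment, so there are two readings.

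*Reading 1: the calls reveal events but do not move the censoring date.* Event-free dropouts in both arms are censored at the last visit, so each arm contributes about 1,040 person-months. Standard-care events are nevertheless found over 1,070. Ratio = (1,040/1,040) / (1,070/1,040) = 1,040/1,070 = 0.97.

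*Reading 2: the calls also move the censoring date.* Standard-care time rises with its events. Ratio = (1,040/1,040) / (1,070/1,070) = 1.00.

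| Loss | Follow-up | Unqueried, intervention | Unqueried, standard care | Reading 1 | Reading 2 |
|---|---|---|---|---|---|
| 10% | 1,140 | 20 | 5 | 1,120/1,135 = 0.99 | 1.00 |
| 20% | 1,080 | 40 | 10 | 1,040/1,070 = 0.97 | 1.00 |
| 30% | 1,020 | 60 | 15 | 960/1,005 = 0.96 | 1.00 |

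**In events.** At 20% loss the calls add 1,070 − 1,040 = 30 person-months of queried time per 100 standard-care patients. The plan gives no event rate. At an assumed annual risk of 10%, that is 30 × 0.10/12 = 0.25 events; at 5% to 15% it is about 0.13 to 0.38.

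**With a common schedule** (months 2, 4, 6, 8, 10, 12) the mean unqueried time per dropout is 2/2 = 1 month. That gives 20 person-months in each arm (1.9%) and a ratio of 1,060/1,060 = 1.00.

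**The case against.** Three things can fairly be said on the other side.

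First, the asymmetry is inferred from silence. Figure 4, the intervention-group flow, and part of the text between sections C.4 and E were not available. Section E.9.1 speaks of regular telephone contact and sets the control group apart only by content. This stands as a limit: a matching intervention call described elsewhere cannot be excluded. The silence still carries some weight. Section E.5.4 takes care to say when messages, video prompts and visits match across arms, and it says nothing of the kind about the monthly call.

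Second, the computed distortion comes from the censoring rule as much as from the calls, and one sentence on censoring would remove it. This is right as far as the rate ratio goes, and it is why the result is given as 0.97 or 1.00. Such a sentence would still leave one arm actively prompted and the other not.

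Third, Aim 3 is exploratory, section E.5.6.2 concedes that the sample is too small for recurrent stroke, and a fraction of an event cannot change a conclusion. This stands too, and it limits the point to a cheap improvement.

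A reader might infer that the calls tilt Aim 3 towards the intervention. Taken alone they would add standard-care events. But section E.5.3.2 has the site call intervention patients after a blood pressure alert, and those calls could bring events to light in that arm. The plan does not support a statement about net direction.

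**Conclusion.** The point holds in a limited form. As the readable plan stands, prompting for Aim 3 events depends on the arm, which sits badly with the aim stated in section E.5.5.3. Under the assumptions above, the null rate ratio at 20% loss is 0.97 or 1.00, depending on an undefined term in the censoring rule. Volunteered reports and alert calls would shrink the effect; poor recall at visits would enlarge it.

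Three wider conclusions are tempting but not supported:
- *That Aim 2 admissions are biased by the calls.* Section E.5.5.2 has a blinded statistician read them from one state database for both arms.
- *That the plan names no adherence measure for comparing the arms.* Section E.5.5.2 names the refill and medication scale, possession ratios and medication counts without restriction to one arm. It only leaves open which of them is the between-arm outcome.
- *That different monitors at remote visits distort the primary blood pressure result.* Section E.5.5.1 applies one assessor-confirmed procedure to both arms. It does not say which monitor either arm uses remotely, and the plan gives neither the share of remote visits nor any device offset. A difference is possible but not shown.

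**What to change.** 1. Put the same short, neutrally worded script on hospitalizations, emergency visits and vascular events to both arms, at the month 2, 6 and 10 calls that all participants already receive and at the 4, 8 and 12-month visits. Neutral wording respects the limit that section E.9.1 sets on control-group contacts.
2. For Aim 3, define the censoring date in both arms as the last answered common script, and count events from common sources only. The standard-care monthly calls may then continue without driving the comparison. Dropping their question instead would discard planned data.
3. Use the blinded discharge-database read already planned for Aim 2 to find unreported Aim 3 admissions in both arms, and send them for adjudication. It does not cover military or federal hospitals, or deaths outside hospital.
4. If a matching intervention call already exists, state it in section E.5.3 with its schedule and questions.

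The cost is a short script on three existing calls, a sentence or two in section E.5.7.1, and slightly more adjudication work. No outcome is dropped.

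Two optional clarifications, separate from this point: designate which of the adherence measures named for both arms is the between-arm outcome, and record visit mode and blood pressure device at each follow-up visit.
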